### 2.3. Primary and secondary objectives:

#### **PICOTS**

**P (problem /population):** geriatric bedridden patients

**I (intervention /indicator):** dissolving Xylitol chewable tablets "listerene ready tabs"

**C (control /comparator):** xylitol chewing gum "Trident original"

**O (outcome) :**

**O1:** salivary streptococcus mutans count

**O2:** interdental plaque bacterial count

**O3:** salivary pH

Type	Outcome Name	Measuring Device	Measuring Unit
1ry	Salivary S.mutans count	Bacterial Culture	CFU/ml
2ry	Interdental plaque Bacterial count	Bacterial Culture	CFU/ml
3ry	Salivary pH	pH Meter	Moles per litre

**T (time):**

**T0:** Baseline

**T1:** 5 minutes

**T2:** 15 days

**S (study):** randomized clinical trial.

## 2) Trial design:

Randomized clinical Trial, parallel arms.

Trial framework: Equivalence frame

Allocation ratio: 1:1.

### **III. METHODS**

#### **A) Participants, interventions, & outcomes**

##### **1) Study Settings:**

This clinical trial will be held in the Faculty of medicine, Cairo University, Egypt.

##### **2) Eligibility criteria:**

###### **a- Eligibility criteria of participants :**

- **Inclusion Criteria :**

- (1) Age range above 65 years old
- (2) Bedridden patients
- (3) Males or females
- (4) Conscious patients
- (5) Co-operative patients approving to participate in the trial.
- (6) Subjects who signed informed consent

- **Exclusion criteria:**

- (1) Individuals had taken antibiotics during the last four weeks or anticipated doing so during the study
- (2) Subjects who wore removable prosthesis
- (3) Patients with systemic diseases that have any oral manifestations
- (4) History of Smoking
- (5) Allergy to any of chewing gum or tablets ingredients
- (6) Evidence of temporomandibular joint disorders
- (7) Presence of intraoral infections
- (8) Currently using any mouth rinse

###### **b- Assessors and operator criteria:**

Operator: M.A. (Master degree),

Assessors: H.M. (Master degree), E.M. (Master degree).

### **3) Interventions:**

In our study, we selected for both intervention and comparator, materials that don't need from those geriatric bedridden patients to leave their beds with both materials are xylitol containing materials but with different delivery system. The intervention is dissolving xylitol chewable tablets and the comparator is xylitol chewing gum.

The intervention is the newly introduced dissolving xylitol chewable tablets " Listerine Ready Tabs ". Technically, it's a rectangular-shaped, bilayer-compressed tablet that once chewed, creates just enough liquid to swish around your mouth to get a whole-mouth clean feeling. As manufacture claimed the tablet is easy to use just in three simple steps: chew (to activate), swish (to clean), then swallow as unlike mouthwashes which may contain alcohol and other ingredients not intended for ingestion, Listerine Ready Tabs are alcohol-free and safe to swallow which is highly suitable for bedridden patients. It's composed of Xylitol, Erythritol, Isomalt, Calcium Carbonate, Flavor, Magnesium Stearate, Cellulose Gum, Hydroxypropyl Cellulose, Tetrasodium Pyrophosphate, PVP, Sucralose, Acacia Senegal Gum, Potassium Acesulfame, Glycerin, and Potassium Sorbate. Moreover the beneficial effect of xylitol ,as mentioned before, the addition of Erythritol in its composition adds more value for the tablets as all studies strongly support the idea of erythritol as a caries-reducing dietary polyol with inhibitory effect on the growth of certain mutans streptococci isolates by a mechanism of growth inhibition differs from that caused by xylitol. Moreover, combinations of erythritol and xylitol will turn out to exert promising caries-limiting effects in humans as the combined effects may exceed or at least equal the separate effects of both polyols. (*Makinen, 2010*)

The comparator is Original Trident which is a soft gum sweetened with xylitol . It also contains sorbitol, Mannitol, Aspartame, Sucralose and Acesulfame potassium.

For our methodology, the saliva and the dental plaque samples will be collected along the previously determined timeline; **T0**: before taking either the intervention or the comparator and **T1**: immediately after 5min and **T2**: 15days (for salivary ph measurement and bacterial count in both saliva and interdental plaque).

- **For Intervention group:**

Participants had to take one tablet three times per day, taken orally, after eating. Participants will be directed to chew the tablet (to activate), swish (to clean), then swallow it . They were not to take other probiotic products or mouth rinse throughout the study period. Neither professional prophylaxis nor tooth brushing instruction will be performed before or during the experimental period. (*Nishihara et al, 2014*)

- **For Comparator group:**

Participants were instructed to chew the gum three times daily after eating for 5 min (*Swapnil et al, 2018*).Also ,like the intervention group, they were not to take other probiotic products or mouth rinse throughout the study period and neither professional prophylaxis nor tooth brushing instruction will be performed .(*Nishihara et al 2014*).

- **Salivary sampling:**

On the day of saliva collection, subjects were instructed not to eat or drink anything for at least 1 hour before the collection of saliva sample. The participants were asked to rinse their mouth with water before

collection of saliva to avoid the contamination of food debris. Then, subjects were instructed to let saliva collect without swallowing for at least 1 min, and then to expectorate into sterile graduated collection tube with the help of a sterile funnel. The collected saliva will be divided into two parts : first; at least 2 ml for ph measurement and second; the remaining salivary sample was transferred into 5-ml sterile disposable vials and carried in a vaccine carrier with freezing mixture to the laboratory, where analysis of the sample was done on the same day. *(Swapnil et al, 2018)*

- **Plaque Sampling:**

Interdental plaque samples were collected from mesial and distal surfaces with the help of a sterile spoon excavator. These plaque samples were then dispersed in a test tube containing double de-ionized distilled water. *(Kumar et al 2013)*

- **Salivary ph measurement:**

The pH values were assessed with the help of a pH meter . The required minimum volume of saliva is 2 ml in a sterile test tube so that the bulb of the measuring electrode could dip sufficiently into the saliva samples. Then, collected samples will be then subjected for the pH measurements. *(Kumar et al 2013)*

- **Culture of mutans streptococci:**

The saliva and plaque sample was homogenized by shaking in a vortex for 30 s to disperse bacterial aggregates. Hundred microliter of saliva and plaque were diluted with 1 ml of sterile peptone water to obtain 1:10 dilution of both saliva and plaque. About 100 µl of the diluted saliva and plaque was further added to 1 ml of sterile peptone water to obtain a

dilution of 1:100. This procedure was repeated to obtain a dilution of 1:1000. This dilution was used for microbial analysis. *S. mutans* will be cultured on mitis salivarius-bacitracin (MSB) agar. The media will be prepared according to the manufacturer's instructions and poured into sterile disposable microbial culture plates and refrigerated till inoculation is done. Under strict aseptic conditions, 5 µl aliquots of each dilution will spread using micropipette onto MSB solid media and sterile glass rod will be used to give homogenous bacterial growth. The MSB agar plate will be incubated for 48 h at 37°C, anaerobically in an atmosphere of 5% CO2 using candle jar. After 48 h of incubation period, *S. mutans* will appear on the culture plate as small, rough, raised, and adherent colonies. Colonies so identified will be counted by a single examiner, who will be unaware of the treatment of the patients. (*Swapnil et al, 2018*)

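### As written, a water rinse falls between the product and the 5-minute saliva sample, so T1 salivary pH and S. mutans count reflect the rinse as well as the product

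*Protocol*

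**What the plan says.** All of the following is in the Protocol. Under III.A, 3) Interventions, T0 is taken "before taking either the intervention or the comparator" and T1 "immediately after 5min"; T2 is at 15 days. The samples serve "for salivary ph measurement and bacterial count in both saliva and interdental plaque". The participant timeline (Table 2) and Outcome data collection (C, 1.2) repeat sampling and assessment at all three times.

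The Salivary sampling paragraph sets one preparation for the day of collection. First, "subjects were instructed not to eat or drink anything for at least 1 hour before the collection of saliva sample". Next, "The participants were asked to rinse their mouth with water before" saliva is collected, in order to clear food debris. Only then does the patient pool saliva for at least a minute and expectorate. No time point is treated differently.

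The tablet group takes "one tablet three times per day, taken orally, after eating" and is told to "chew the tablet (to activate), swish (to clean), then swallow it". The gum group is to "chew the gum three times daily after eating for 5 min".

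The aim (2.1) presents both products as a substitute for brushing and rinsing. Both arms are active; there is no untreated arm (PICOTS; Trial design).

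**The concern.** The preparation suits a resting sample such as T0 or T2. T1 is different, because it is meant to capture what the product has done in the mouth within minutes. A rinse at that moment intervenes on the same fluid that is about to be measured.

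The Protocol itself describes both products as acting partly through fluid in the mouth. Under Choice of comparator (1.5), gum is credited with clearing acid by stimulating saliva. Under Interventions, the tablet is said to produce a liquid that is swished around. A water rinse can imitate or overwrite that action.

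Salivary S. mutans count is the primary outcome and is measured at T1. The outcome tables name no primary time point, so T1 cannot simply be set aside as minor. If the T1 reading mixes two causes, a fall in count or a change in pH from T0 could be reported as a product effect when part of it is water. Samples collected this way cannot be corrected afterwards.

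**Working it through.** The plan states no figure for this point, so there is none to reproduce. The check sets the instructions in order and works out what follows.

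**1. Order of events at T1.** Product, then a 5-minute wait, then T1 saliva. The saliva procedure is: no intake for 1 hour, rinse, pool for at least 1 minute, expectorate. Since pooling follows the rinse, the rinse comes directly before collection. Applied to T1, the order is T0 rinse, T0 sample, product, second rinse, T1 sample.

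**2. T0 to T1 change in count.** Let the product multiply the salivary count by p, and let the second rinse remove a share r. The T0 sample already carries the first rinse, so on the log10 scale

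change = log10(p) + log10(1 − r).

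With no untreated arm, p and r cannot be separated. The Protocol gives no value of r, so the following shares are assumptions that only show the range:

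| Share removed, r | Fall in log10 count due to rinse, −log10(1 − r) |
|---|---|
| 10% | 0.05 |
| 25% | 0.12 |
| 50% | 0.30 |
| 75% | 0.60 |
| 90% | 1.00 |

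The outcome categories (Table 1) are tenfold apart, so a full category step from the rinse alone needs 90% removal. Smaller shares still move patients who lie near a boundary.

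**3. Between-arm contrast in count.** If r is the same in both arms, the difference is

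[log10(p₁) + log10(1 − r)] − [log10(p₂) + log10(1 − r)] = log10(p₁) − log10(p₂).

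The rinse cancels. The contrast changes only if the rinse acts differently by arm, for instance by removing residual product that would otherwise go on acting.

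**4. Between-arm contrast in pH.** This cancellation does not carry over to pH. Adding the same water to saliva in both arms may draw the two readings together. The rinse volume, its interval before sampling and the size of any product effect are not given, so the amount cannot be computed.

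**5. The 1-hour rule at T1.** Let g be the minutes from food to product. Food to T1 is g + 5, or g + 10 if the 5 minutes starts after a 5-minute chew.

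- Product directly after a meal (g = 0): 5 or 10 minutes, against 60 required. The rule is broken.
- The rule is met when g is at least 60 − 5 = 55 minutes, or 60 − 10 = 50 minutes on the later clock.
- If T0, product and T1 run in one session, the fast for T0 is at least 60 minutes, so T1 is at least 60 + 5 = 65 minutes after food. The rule is met.
- If the swallowed tablet itself counts as intake, T1 is 5 minutes after intake, and the rule fails in the tablet arm whatever g is.

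The Protocol does not say which of these applies, nor when the 5 minutes starts.

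**6. Scope.** T2 has no product-to-sample interval of this kind. The Plaque Sampling paragraph contains neither a fast nor a rinse. The point concerns saliva at T1.

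**The case against.** The strongest reply is that the preparation is framed by day. T0 and T1 fall in one session, and the rinse is there to clear food debris. With no food described between the two samples, one fast and one rinse before T0 would serve both, and the after-eating instruction belongs to the daily regimen. On that reading nothing goes wrong.

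Much of this stands for the fast. A reader might infer that T1 can never comply with the 1-hour rule; step 5 shows that it can, in a single fasted session with the product exempt. It stands less well for the rinse. The text places the rinse before saliva collection, T1 is a saliva collection, and nothing says the T0 rinse covers both. Staff who follow the text will rinse again.

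A reader might also infer that the rinse abolishes the acute effect, or must shrink any difference between arms and so favour a finding of no difference in a trial labelled as equivalence. The document supports neither. Equal proportional removal leaves the log-count difference unchanged (step 3), and no rinse volume or effect size is given. For the same reason, any statement of how many more patients would be needed would rest on an invented attenuation. The sample size section does not concern a 5-minute effect in any case.

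**Conclusion.** The point holds for T1 saliva. The plan as written puts a water rinse between product and sample, which confounds the T0 to T1 change in salivary pH and S. mutans count. It may dilute the between-arm contrast, most plausibly for pH. The size cannot be computed from the document; the log10 shifts of 0.05 to 1.00 rest on assumed removal of 10% to 90% and are illustrations only.

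The no-intake rule is in tension with a swallowed tablet and with dosing after eating, but this is a matter to reconcile, not an impossibility. The conclusion assumes that staff apply the written procedure at every saliva collection.

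**What to change.** Reconcile the T0/T1/T2 timeline and the Salivary sampling paragraph under III.A, 3) Interventions, by time point:

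- Apply the 1-hour fast and the water rinse before T0 and before T2.
- Run T0, product and T1 as one session, with no food, drink or rinse between the T0 and T1 samples, so that the T0 preparation covers both.
- State that the study product is exempt from the no-intake rule for sampling.
- State when the 5 minutes starts: at the start or at the end of product use.

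The investigators should also state how product use in that session relates to the after-eating instruction, since the two passages now pull apart.

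The cost is a few sentences, with no extra visit or staff. The downside is small: T1 saliva may contain some product residue.

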solution and their scores were recorded at six sites per tooth using the Quigley and Hein plaque index modified by Turesky-Gilmore-Glickman. They found that the mean plaque scores for Groups I, II and III were 1.37, 1.35 and 1.57, respectively. The ANOVA revealed that between group comparison was significant, with an F-value of 5.99 and a probability value of 0.004. The T-test was carried out to evaluate the inter-group significance, which revealed that the plaque inhibition by Manuka honey was similar to that of chlorhexidine mouthwash. So they concluded that both Manuka honey and chlorhexidine mouthwash reduced plaque formation significantly, better than the xylitol chewing gum.

*Kumar, et al in 2013*, evaluated the salivary and dental plaque pH changes after consumption of sugared and sugar-free (xylitol) chewing gums in children. They selected a total of 30 school children for this study and divided them into two equal groups and gave both chewing gums for the experiment. They found that children consuming the sugar-free (xylitol) chewing gum showed a marked increase in the pH of saliva and plaque when compared to their counterpart. All these values had a significant difference of  $P \leq 0.0001$ . So, they concluded that xylitol is a safe natural sweetener which helps to reduce tooth decay. It plays a unique role in preventive strategies for better health.

*Nishihara et al in 2014* evaluated the effects of the lactic acid bacterium *Lactobacillus salivarius* on caries risk factors. They performed their study in 64 healthy volunteers to evaluate the effects of *L. salivarius*-containing tablets on caries risk factors. They divided participants randomly into four groups, and gave them chewable tablets containing *L. salivarius* WB21, *L. salivarius* TI 2711, Ovalgen® DC (antibody against glucosyltransferase from *Streptococcus mutans*), or

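### Plaque for a viable culture count is held in de-ionized distilled water, a step taken from a plaque pH study, and the carriage and same-day rule is written only for saliva

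*Protocol*

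**What the plan says.** Under III.A 3) Interventions, Plaque Sampling, interdental plaque is taken with a sterile excavator and then: "These plaque samples were then dispersed in a test tube containing double de-ionized distilled water". Neither the tube nor the water is described as sterile, and no volume is given. The source cited is the 2013 study of gum in children. Section 1.4, Review of literature, says that this study "evaluated the salivary and dental plaque pH changes after consumption of sugared and sugar-free (xylitol) chewing gums in children".

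The outcome list in section 2.3 has "O2: interdental plaque bacterial count", by culture in CFU/ml, as the second-ranked outcome. The only pH outcome is "O3: salivary pH".

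Under Salivary sampling, the rule for the part of the saliva not used for pH is that "the remaining salivary sample was transferred into 5-ml sterile disposable vials and carried in a vaccine carrier with freezing mixture to the laboratory". The same paragraph also calls for this saliva to be analysed within the day of collection. No such rule is written for plaque. The next step stated for plaque is the laboratory work under Culture of mutans streptococci: vortexing, and then "Hundred microliter of saliva and plaque were diluted with 1 ml of sterile peptone water".

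**The concern.** A culture count includes only organisms still alive at plating. Pure water suits a pH reading because it adds no buffer, but it puts live cells under osmotic stress. That is general laboratory reasoning; the protocol does not discuss it. A step described as serving a pH measurement has been carried into an outcome that depends on survival, and it covers the one interval, from collection to bench, for which the plan sets no temperature or time limit for plaque.

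If cells are lost in that interval, the plaque count reflects handling time as well as the product. Unequal handling times add variance. A large loss pushes samples from both arms towards the lowest grade and so compresses the difference between them. If the delay differed between baseline and day 15, part of the within-arm change would be an artefact.

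**Working it through.** The plan states no figure on this point, so there is none to reproduce. The check has two parts.

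**1. The text, side by side**

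| Item | Saliva for culture | Plaque for culture |
|---|---|---|
| Container | sterile vial | test tube, sterility not stated |
| Holding medium | none added | de-ionized distilled water |
| Carriage | vaccine carrier with freezing mixture | not stated |
| Time limit | same day | not stated |
| Laboratory diluent | sterile peptone water | sterile peptone water |

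The water step precedes the peptone dilution, so it spans the time between collection and bench. Section C 1.3, Patient retention, has the operator visit patients for sampling, and the administrative section places the bacteriology in the microbiology department. The plan therefore does not hold this time constant, although nothing shows how much it varies.

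**2. What a loss would do (illustration; rates and times are assumed)**

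Loss in log10 units = −log10(1 − fraction lost).
- 20% lost: −log10(0.80) = 0.10.
- 90% lost: −log10(0.10) = 1.0.

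Grades in Table 1 are 1.0 log10 apart.

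For the effect on grades, I borrowed the probabilities in the sample size section, which are for salivary counts: 0.15/0.60/0.25 for gum and 0.35/0.50/0.15 for tablets. A normal distribution of log10 counts was fitted to each arm, with cuts midway between powers of ten:
- Gum: SD = 1/(z(0.75) − z(0.15)) = 1/(0.674 + 1.036) = 0.584; mean = 2.5 + 1.036 × 0.584 = 3.11.
- Tablet: SD = 1/(z(0.85) − z(0.35)) = 1/(1.036 + 0.385) = 0.703; mean = 2.5 + 0.385 × 0.703 = 2.77.

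Loss = rate × time, with time uniform over 0 to 6 hours and the same distribution in both arms (400,000 simulated samples per arm).

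| Rate (log10/h) | Largest loss (6 × rate) | Gum samples moved down a grade | Gum in lowest grade | Tablet in lowest grade | Gap (points) |
|---|---|---|---|---|---|
| 0 | 0 | 0% | 15.0% | 34.9% | 19.9 |
| 0.05 | 0.3 | 14.5% | 21.9% | 43.2% | 21.3 |
| 0.1 | 0.6 | 28.7% | 30.7% | 51.6% | 20.9 |
| 0.2 | 1.2 | 52.2% | 49.7% | 66.1% | 16.4 |
| 0.4 | 2.4 | 68.6% | 72.8% | 81.9% | 9.1 |

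Hand check of the gum figure at 0.2 log10/h, using the mean time of 3 h: Φ((2.5 + 0.6 − 3.106)/0.584) = Φ(−0.01) ≈ 0.50, in line with 49.7%.

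The gap in the lowest grade is about unchanged at the two lower rates and shrinks at the two higher ones. The apparent level in each arm moves at every non-zero rate.

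**The case against.** The strongest reply is that the documents give no survival rate and no transport time, so a material loss is inferred, not shown. This stands. A reader might infer that the count will fall and that time in water will vary; the text supports only that both may happen and that the plan does not control them. Table 2 names no place of sampling, and recruitment and microbiology are both in the Faculty of Medicine, so delays could be short and similar.

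A reader might also infer bias towards one product. The documents do not support that. The arms are randomised, share one schedule and one sampling operator, and have their colonies counted by one examiner unaware of treatment, so any loss should be similar in both. In the illustration the contrast shrinks only at the higher assumed rates.

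A third reply is that saliva and plaque are taken at the same time points by the same person and processed in the same laboratory steps, so both tubes probably travel together. That is plausible and would make the carriage gap a matter of wording. It does not dispose of the medium, which the protocol names. For the same reason a laboratory manual could not quietly cure it: a manual that specified a culture medium would contradict the protocol.

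Finally, one might argue that different handling makes saliva and plaque counts non-comparable. No such comparison is planned, so that is not part of this point.

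**Conclusion.** The point holds as a modest, cheaply corrected flaw in the second-ranked outcome. Three things rest on the text alone: the medium, its origin in a study described as one of pH, and handling rules written for saliva but not for plaque. The consequence rests on general knowledge that salt-free water keeps live cells poorly. The count may fall with time to plating, which would mainly add noise, could dilute the contrast between arms, and could cloud within-arm change if delay differs between visits.

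The size is unknown. The range of 0.10 to 1.0 log10 is an assumption. A shift of a full grade for every sample needs the 90% extreme, and it presumes that the Table 1 grades apply to plaque. Neither a certain loss nor an advantage to one product should be claimed. The primary outcome, the salivary count, is not affected.

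**What to change.** In the Plaque Sampling paragraph:
- Replace the de-ionized distilled water with a stated, fixed volume of the sterile peptone water already used for the dilutions, in a sterile tube.
- State that the saliva rule (cold carrier, analysis on the same day) also applies to plaque, with one maximum time from collection to plating at all visits.
- Record the collection and plating times for each sample, so that the delay can be described by arm and visit.

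Fixing the volume also gives the plaque CFU/ml a defined liquid volume, which it now lacks; the amount of plaque collected would still be unstandardised.

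The cost is a few sentences and the pre-filling of sterile tubes. The peptone water and cold carrier are already in use. The change has to be made before sampling starts, because lost viability cannot be recovered in the analysis.

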## ***I) Administrative information***

- 1) **Title:** " Effect of Dissolving Xylitol Chewable Tablets versus Xylitol Chewing Gum with Geriatric Bedridden Patients on Salivary pH and Bacterial Count in Both Saliva & Interdental Plaque :  
Randomized Clinical Trial"
- 2) **Trial registration:** Trial will be registered in <https://clinicaltrials.gov/>
- 3) **Protocol version:** This is the first version of the protocol (March 2019).
- 4) **Funding:** No funding from any parties
- 5) **Trial sponsor:** Faculty of Dentistry, Cairo University.
- 6) **Roles and responsibilities:**

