### 1) Outcomes: (*Table 1*)

No.	Outcome Name	score	Criteria	type	Methods of aggregation
1ry	Salivary S.mutans count	VL: very low	10  cfu/ml	Categorical ordinal	Absolute risk will be reported for each intervention independently. Relative risk will be used to compare both interventions with 95 % CI.
		L: low	10  cfu/ml		
M: Moderate	10  cfu/ml				
H: High	10  cfu/ml				
2ry	Interdental plaque Bacterial count	Swapnil et al, 2018			
3ry	Salivary ph	Numerical values	Normal salivary ph = 6.2 - 7.6	Continous	Mean and Standard deviation
		Baliga et al, 2013			

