## 2) Participant timeline: (Table 2)

Activity	Staff member	T0 Baseline	T1 After 5 min	T2 After 15 days
Recruitment	Y.S.	X		
Diagnosis	Y.S.	X		
Consent	Y.S.	X		
Baseline data collection	Y.S.	X		
Randomization	Y.S.	X		
Saliva & Plaque sampling	M.A.	X	X	X
Outcome assessment	H.M. E.M.	X	X	X

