## 3) Sample size calculation:

A power analysis was designed to have adequate power to apply statistical test of the research hypothesis that dissolving xylitol chewing tablets will have the better antibacterial effect than xylitol chewing gum against mutans streptococci after 1 month. According to the results of *Swapnil et al. in 2018* in which the probability of bacterial count reduction to  $10^2$  for xylitol chewing gum (comparator) was (0.15), probability of bacterial count reduction to  $10^3$  was (0.6) and probability of bacterial count reduction to  $10^4$  was (0.25) with effect size  $w=0.578$  ( $n=29$ ). If the estimated probability of dissolving xylitol chewing tablets for bacterial count reduction to  $10^2$  is (0.35), probability of bacterial count reduction to  $10^3$  is (0.5) and probability of bacterial count

reduction to  $10^4$  was (0.15) with effect size  $w=0.43$  ( $n=53$ ). By adopting an alpha ( $\alpha$ ) level of 0.05 (5%), power=80%. The predicted sample size ( $n$ ) was a total of (82). Sample size was increased by (20%) to account for possible dropouts during follow-up intervals to be total of (98) cases i.e. (49) for each group. Sample size calculation was performed using G\*Power 3.1.9.2.

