### **3) Statistical methods:**

Data will be analyzed using IBM SPSS advanced statistics (Statistical Package for Social Sciences), version 25 (SPSS Inc., Chicago, IL). Categorical data will be described as absolute risk for each intervention independently and relative risk when comparing both interventions. Comparisons between categorical variables will be performed using the chi square test and Kruskal Wallis will be used to test interaction of variables. Continuous data will be described using mean and standard deviation. Comparison between continuous data will be performed using t-test and two-way ANOVA will be used to test interaction of variables. A p-value less than or equal to 0.05 will be considered statistically significant and all tests will be two tailed.

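### The plating scheme cannot produce a non-zero count at the lowest grade of the primary outcome and cannot reliably separate the two lowest grades

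*Protocol*

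**What the plan says.** Under Interventions, in the paragraph on culture of mutans streptococci, 100 µl of sample goes into 1 ml of peptone water for a nominal 1:10 dilution, and the step is repeated to 1:100 and 1:1000. The text continues: "This procedure was repeated to obtain a dilution of 1:1000. This dilution was used for microbial analysis". A few lines later, 5 µl "aliquots of each dilution will spread using micropipette onto MSB solid media". The two sentences disagree on whether one dilution or all three are plated. The protocol mentions no undiluted plate, larger volume, replicate plates, detection limit or rule for a plate without growth.

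Outcomes (Table 1) makes the salivary *S. mutans* count the primary outcome. It is an ordinal grade at 10² (very low), 10³ (low), 10⁴ (moderate) and 10⁵ (high) CFU/ml, and the table does not say whether these are points or ranges. Table 1 adds "Relative risk will be used to compare both interventions" without naming the grade or cut-point. Under Statistical methods: "Comparisons between categorical variables will be performed using the chi square test".

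The sample size section assumes proportions at 10², 10³ and 10⁴ of 0.15, 0.60 and 0.25 for gum and 0.35, 0.50 and 0.15 for tablets.

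**The concern.** The volume plated and the lowest dilution fix the smallest concentration an assay can report. Here that floor lies above the two lowest grades of the primary outcome. Those grades hold most of the assumed patients, and the assumed benefit is mainly a shift into the lowest one (0.15 against 0.35).

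If the two grades merge, the chi-square test loses power and a relative risk for the lowest grade is pulled toward 1. The Trial design section calls this an equivalence trial, so such dilution could pass for similarity. It cannot be repaired at the analysis stage, because saliva that was never plated yields no colonies.

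**Working it through.** **Inputs.** Plated volume 0.005 ml; nominal dilutions 10, 100 and 1000 (Interventions). Grades 10² to 10⁵ CFU/ml (Table 1). Proportions as above, and 41 or 49 patients per arm, from 82 and 98 in total (Sample size calculation).

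**The plan's own figure.** The total of 82 reproduces as two separate goodness-of-fit tests, each arm against equal thirds with 2 degrees of freedom: w = 0.579 gives 29 and w = 0.430 gives 53; 29 + 53 = 82, and 82 × 1.2 = 98.4, stated as 98. This is not the planned comparison between arms. On the same proportions that comparison has w = 0.239 and power of about 48% at 41 per arm and 55–56% at 49. The gap from the stated 80% is a separate sample-size problem; only the loss below 48–56% is counted here.

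**Value of one colony.** CFU/ml per colony = dilution / 0.005:
- 1:10 plate: 2,000
- 1:100 plate: 20,000
- 1:1000 plate: 200,000

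Taken literally, 0.1 ml into 1 ml is 1:11, which gives 2,200 on the first plate. Pooling all three nominal plates gives 1/(0.005 × 0.111) = about 1,800. Neither changes the conclusion.

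**Chance of an empty plate.** With Poisson plating, P(0) = exp(−c × 0.005 / dilution) for concentration c:

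| True CFU/ml | 1:10: expected colonies | 1:10: P(0) | 1:1000: P(0) |
|---|---|---|---|
| 10² | 0.05 | 95% | 99.95% |
| 10³ | 0.5 | 61% | 99.5% |
| 10⁴ | 5 | 0.7% | 95% |
| 10⁵ | 50 | about 0 | 61% |

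The two upper grades are countable on the 1:10 plate.

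**Effect on the comparison, 1:10 plate, no growth scored as very low.** Grades as points:
- Gum observed at the lowest grade: 0.15 × 0.951 + 0.60 × 0.607 + 0.25 × 0.007 = 0.508
- Tablet: 0.35 × 0.951 + 0.50 × 0.607 + 0.15 × 0.007 = 0.637
- Relative risk: 0.637 / 0.508 = 1.25, against a true 0.35 / 0.15 = 2.33

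Grades as decades, with concentrations log-uniform within each: 27% against 41% empty, relative risk 1.52. Correct grading is then 83% for very low, 65% for low, 91% for moderate and 98% for high.

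The relative risk for 10⁴ or above moves little, from 0.15 / 0.25 = 0.60 to 0.64 (points) or 0.65 (decades).

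**Chi-square power (simulation, 20,000–40,000 trials):**

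| Grading | 41 per arm | 49 per arm |
|---|---|---|
| Perfect | 0.48 | 0.56 |
| 1:10 plate, points | 0.19 | 0.22 |
| 1:10 plate, decades | 0.23 | 0.26–0.27 |

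**Only the 1:1000 plate counted.** Empty plates, gum and tablet: 98.5% and 99.0% (points), or 94.5% and 96.4% (decades). The lowest-grade relative risk is 1.005 or 1.02, so almost no information is left.

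**Higher counts.** The proportions are planned for a "better antibacterial effect than xylitol chewing gum against mutans streptococci after 1 month", but the last sample is "T2 After 15 days". If half the patients were one grade higher, the lowest-grade relative risk would be 1.41–1.62 instead of 2.33, and power at 49 per arm 21–22% instead of 29–30%. If all were one grade higher, power would be 38–41% instead of 56%.

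**The case against.** The strongest objection concerns the planning proportions. The plating method, the grades and the gum proportions are all credited to the same 2018 gum study. If that study plated this way, its proportions already contain the misclassification, and applying it again counts part of the loss twice. This stands as a limit on the power and relative-risk figures and cannot be settled from the protocol. It does not touch the 2,000 CFU/ml floor.

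Second, an ordinal lowest class may properly include samples without growth. That is so, and the calculation scores them that way. The damage then comes mainly from samples at 10³ falling into very low. The 61% applies at exactly 10³; on the decade reading 65% of low samples are graded correctly, which is milder but still poor.

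Third, the source study enrolled students, while this trial enrols bedridden patients over 65. Their counts may be higher, and the loss would then be smaller, as the last step of the working shows. A relative risk cut at 10⁴ would barely suffer, but the protocol does not choose that cut.

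Fourth, the grading rule for no growth and the cut-point could be left to an analysis plan. That is fair for those two items, but not for the plated volume and dilution, which the protocol fixes. Finally, the same assay serves both arms and the colony counter is unaware of treatment, so under a true null the harm is attenuation and not a raised false-positive rate.

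**Conclusion.** The concern holds and should be fixed before sampling starts. The firm part is arithmetic on the protocol's own figures. One colony is worth at least 2,000 CFU/ml on any single listed plate, 20 times the lowest grade and twice the next. The text also contradicts itself on a point that changes this floor a hundredfold.

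The drop in lowest-grade relative risk to 1.25–1.52 and in power to about 19–27% is a conditional illustration. It assumes that the planning proportions are true concentrations, that plating is Poisson, and that no growth is graded very low. It would be smaller if counts run higher or if the source study shared this plating.

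**What to change.** In the culture paragraph, reconcile the two sentences and state which dilutions are counted. Choose the plated volume and lowest dilution so that one colony is below 10² CFU/ml. One example is a 100 µl plate of undiluted saliva (1/0.1 = 10 CFU/ml per colony), preferably with a 100 µl plate of the 1:10 dilution (10/0.1 = 100 CFU/ml per colony) to bridge to the existing plates. Other laboratory designs would also serve, but 5 µl of undiluted saliva would not (1/0.005 = 200 CFU/ml per colony). State the detection limit and how no growth is graded. In Table 1, define the grades as ranges and name the grade or cut-point for the relative risk.

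Counting the most sensitive plate with at most 300 colonies (an assumed limit), and with grades as decades:
- Undiluted plate only: lowest-grade relative risk 2.04; power 0.39 at 41 per arm and 0.45 at 49.
- Both plates: relative risk 2.24; power 0.43 and 0.50; correct grading 96–98%.

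With grades as points, either option restores almost everything (relative risk 2.31–2.33; power 0.48 and 0.56). The underlying sample-size shortfall remains.

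The cost is 98 patients × 3 time points = 294 saliva samples, so 294 to 588 extra plates plus counting time, in a trial with "No funding from any parties". Doing the same for plaque would double this. No extra visits are needed. The undiluted plate uses a further 0.1 ml of saliva. The laboratory should confirm that this is available after the 2 ml set aside for pH.
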